### 3.6.2 Clinical Laboratory Tests

Clinical laboratory assessments are listed in Appendix B of the Clinical Study Protocol and will be summarized using descriptive statistics at the scheduled visits and/or timepoints that are specified within the Schedule of Events within the Protocol. A list of laboratory tests to be performed is included within the protocol.

Observed values and change from baseline will be presented at each scheduled visit and/or timepoint and baseline by laboratory test. The incidence of abnormalities (as defined by normal ranges) prior to the first dose of study drug and after the first dose of study drug will be summarized with counts and percentages of subjects.

All laboratory data will be summarized using the International System of Units (SI).

All laboratory data will be listed.

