14. A positive response to either Question 4 or Question 5 on the Suicidal Ideation portion of the Columbia-Suicide Severity Rating Scale (C-SSRS) or a positive response to any of the suicide-related behaviors on the Suicidal Behavior portion of the C-SSRS at Screening or Check-In;

Note: A subject should be referred to a mental health professional if she has any suicidal ideation of Type 4 or 5 on the C-SSRS at any time during the study.

15. A baseline score >15 on the Patient Health Questionnaire 9 (PHQ-9) at Screening or Check-In;
16. A history of Major Depressive Disorder within the last 2 years;
17. Any lifetime history of a suicide attempt;
18. A history of other severe psychiatric disorders (eg, schizophrenia, bipolar disorder);
19. Previous bariatric surgery, procedure for obesity, or GI surgery altering GI passage, motility, and/or nutrient absorption or recent (within 6 months of Screening) changes in body weight ( $\geq 5\%$ ) due to dieting, including commercial weight loss programs, or pharmacologic treatment;
20. Currently on or planning to participate in any weight loss regimen during the course of the study;
21. Personal or family history of medullary thyroid carcinoma or multiple endocrine neoplasia type 2;
22. History of malignancy, except the following: curatively resected basal cell or squamous cell skin cancers, cervical cancer in situ, or resected colorectal polyps >5 years prior to Screening;
23. Abnormal fasting blood glucose (ie, >125 mg/dL) at Screening or Check-In and/or glycated hemoglobin (HbA1c) (ie, >6.4%) at Screening, or prior history/diagnosis of any type of diabetes mellitus (eg, type 1, type 2, or gestational);
24. Alanine aminotransferase, aspartate aminotransferase, alkaline phosphatase, and/or total bilirubin above the central laboratory's upper limit of normal (ULN); fasting triglycerides >500 mg/dL; impaired renal function with estimated glomerular filtration rate <90 mL/min/1.73 m^2 at Screening or Check-In; or calcitonin above the central laboratory's ULN at Screening;
25. Any other clinical laboratory values that are meaningfully outside of normal limits (based on laboratory normal range) at Screening or Check-In in the opinion of the Investigator;
26. Positive for HIV antibody, hepatitis C virus (HCV) antibody, or hepatitis B surface antigen at Screening;
27. Positive COVID-19 test at Check-In;

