| Serum FSH l  | X         |                |                  |   |   |   |   |   |   |                   |                         |
| SARS-CoV-2 testing m   |           | X              |                  |   |   |   |   |   |   |                   |                         |
| 12-lead ECG n  | X         | X              | X                |   |   |   |   |   |   | X                 |                         |
| Chemistry (including total cholesterol
and triglycerides), hematology,
coagulation o | X         | X              | X                |   | X |   | X |   | X |                   |                         |
| TSH, calcitonin, HbA1c o   | X         |                |                  |   |   |   |   |   | X |                   |                         |
| Urinalysis  | X         | X              | X                |   | X |   | X |   | X |                   |                         |
| PK p   |           |                | X                |   | X |   | X |   | X |                   |                         |
| Admission/discharge   |           | Admission      |                  |   |   |   |   |   |   | Discharge         |                         |
| Randomization q  |           |                | X                |   |   |   |   |   |   |                   |                         |
| Study drug administration r  |           |                | X                | X | X | X | X | X | X |                   |                         |
| Injection site reaction s  |           |                | X                | X | X | X | X | X | X |                   |                         |
| Food intake (weight, energy content) t   |           |                | X                | X | X | X | X | X | X |                   |                         |

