| 
When several assessments are required at the same time point, evaluations should be completed so that the PK sample is collected at the required time. It is understood that other assessments such as ECGs, vital signs, etc will be performed as close to the actual time as possible but may be collected earlier or later than the actual time point.
 
a. If a subject withdraws prematurely from the study for any reason, study staff should make every effort to complete the full panel of assessments scheduled for Day 8/ET. The reason for subject withdrawal must be documented in the eCRF.
 
b. Signed informed consent must be obtained before any study-related procedures are performed.
 
c. Subjects meeting eligibility criteria at Screening and Check-In will be randomized into the study pre-dose on Day 1.
 
d. Any updates since Screening will be assessed.
 
e. Any medications administered within 6 months prior to the first dose of study drug and during the study must be recorded in the eCRF.
 
f. Height will be collected at the Screening Visit only and will be used to calculate BMI at Screening only. Body weight should be measured while the subjects are wearing a gown or light indoor clothing without shoes, while fasting for at least 10 hours, and after voiding. Body weight measurements should be done in a consistent manner using a calibrated electronic scale capable of measuring weight in kilograms to 1 decimal place.
 
g. A full physical examination (including head, eyes, ears, nose, and throat; cardiovascular; respiratory; gastrointestinal; neurological; dermatological; and musculoskeletal systems) will be performed at Screening. Symptom-based physical examinations will be performed at Check-In, Day 1 pre-dose, and Day 8/ET.
 
h. Vital signs include temperature, respiratory rate, heart rate, and blood pressure. Vital signs will be performed with the subject in a seated position after at least a 5-minute seated rest. Vital signs will be assessed at Screening; Check-In; pre-dose, 1 hour post-dose, and 6.5 hours post-dose on Days 1 through 7; and on Day 8/ET. Abnormal vital signs may be repeated no more than 1 time for eligibility purposes.
 
i. A urine screen for drugs of abuse, a urine cotinine test, and a breath alcohol screen will be performed for all subjects.
 
j. The “Baseline” C-SSRS questionnaire will be administered during the Screening Period. At all other visits, subjects will be given the “Since Last Visit” questionnaire.
 
k. A serum pregnancy test will be performed for all subjects during the Screening Period and at Check-In.
 
l. A serum FSH test will be performed at Screening for subjects who are postmenopausal (ie, have experienced spontaneous amenorrhea for at least 2 years).
 
m. A test for SARS-CoV-2 will be administered to subjects at the study site on Day -1 prior to admission. Subjects testing positive for COVID-19 are not eligible for the study.
 
n. All 12-lead ECGs will be performed in triplicate approximately 1 minute apart after the subject has been resting in the supine position for at least 10 minutes. On Day 1, ECG should be performed approximately 1 hour post-dose.
 
o. Subjects are required to fast overnight (ie, no food or beverage [except water]) for at least 10 hours. All evaluations should be obtained prior to study drug administration. Abnormal laboratory tests may be repeated no more than 1 time for eligibility purposes.
 
p. Blood samples will be collected to evaluate PK on Days 1 and 7 at pre-dose (within 30 minutes prior to study drug administration) and 10, 20, 30, 45, 60, 120 and 180 minutes post-dose. The following windows will be permitted for the collection of post-dose PK samples: within ±5 minutes of the nominal time up to and including the 45 minutes sample and within ±10 minutes for samples collected 60, 120, and 180 minutes post-dose. In addition, pre-dose samples will be collected on Days 3 and 5 (within 30 minutes prior to study drug administration).
 
q. Randomization will occur after all Check-In assessments are performed and results are reviewed at pre-dose on Day 1 to confirm and verify that the subject meets all inclusion and no exclusion criteria. All subjects will be randomized to 1 of the 3 parallel treatment groups in a 3:3:2 ratio to receive ROSE-010 99 mcg, ROSE-010 150 mcg, or placebo, respectively.
 |           |                |                  |   |   |   |   |   |   |                   |                         |

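### The SAP's before/after laboratory abnormality count sets eligibility-filtered pre-dose values against unfiltered post-dose values, so for a few analytes the within-arm incidence is expected to rise with no drug effect

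*SAP*

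**What the plan says.** SAP 3.6.2 plans counts and percentages of subjects for "The incidence of abnormalities (as defined by normal ranges) prior to the first dose of study drug and after the first dose of study drug". It also plans observed values and change from baseline at each scheduled visit, and a listing of all laboratory data. SAP 3.1.4 presents data by treatment, placebo included.

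Protocol Section 4.2, Exclusion 24, bars subjects with "Alanine aminotransferase, aspartate aminotransferase, alkaline phosphatase, and/or total bilirubin above the central laboratory's upper limit of normal (ULN"). After further clauses on triglycerides and renal function, it bars those with "calcitonin above the central laboratory's ULN at Screening". Exclusion 11 concerns uncontrolled thyroid disease and refers to TSH outside the normal range at Screening.

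Appendix A, Table 2 fixes the draws. The row beginning "Chemistry (including total cholesterol" is marked at Screening, Check-In and Days 1, 3, 5 and 7. The row "TSH, calcitonin, HbA1c" is marked at Screening and Day 7 only. Footnote o, attached to both rows, says "All evaluations should be obtained prior to study drug administration" and allows one repeat of an abnormal test for eligibility. Footnote c says "Subjects meeting eligibility criteria at Screening and Check-In will be randomized into the study pre-dose on Day 1".

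**The concern.** The chemistry panel has three draws before the first dose (Screening, Check-In, Day 1) and three after it (Days 3, 5, 7). Subjects who were high on an eligibility draw are not in the trial, so those draws contribute few or no high values to the pre-dose count. The post-dose draws carry no such filter. Calcitonin has one pre-dose draw, which is the eligibility draw, and one post-dose draw.

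A reader who compares the two columns within an arm could take the expected rise for a hepatic or calcitonin signal. What is at stake is the reading of a descriptive safety table. The SAP plans no test of before against after, and no stated decision rests on it.

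**Working it through.** The plan states no laboratory abnormality rate, so there is no figure of its own to reproduce. The question is how large the rise would be with no drug effect.

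**Inputs from the documents.** Three chemistry draws before and three after first dose; one calcitonin draw before and one after (Table 2). Exclusion at the ULN (Exclusion 24). One repeat allowed (protocol Section 4; Table 2, footnote o). Arms of 15, 15 and 10 (protocol Section 3.1).

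**Assumptions not in the documents.** Probability *p* of a value above ULN at each draw: 2.5%, 5% or 10%. Exchangeable within-subject correlation from 0 to 0.9 on a latent normal scale. No drug effect. The liver tests are screened at both Screening and Check-In unless stated. In the repeat variants, every abnormal eligibility value is repeated once.

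**Step 1: independent draws, *p* = 2.5%, by hand.**
- Post-dose, any of three draws high: 1 − 0.975³ = 7.3%. Without selection the pre-dose figure would be the same.
- Pre-dose, no repeats: only Day 1 can be high, so 2.5%. Ratio 7.3/2.5 = 2.9.
- Pre-dose, one repeat, first value kept: among those who pass, the chance that the first value was high is *p*/(1 + *p*) = 0.025/1.025 = 2.44%. Then 1 − 0.9756² × 0.975 = 7.2%. Ratio 7.3/7.2 = 1.02.
- Pre-dose, liver tests screened at Screening only, no repeats: 1 − 0.975² = 4.9%. Ratio 7.3/4.9 = 1.5.

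**Step 2: correlated draws, by simulation.** For one liver analyte at *p* = 5% and correlation 0.7:

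| Which pre-dose values count | Before | After | Ratio |
|---|---|---|---|
| No eligibility filter | 10.3% | 10.3% | 1.0 |
| Filter, no repeats | 2.4% | 5.9% | 2.5 |
| Filter, one repeat, only the repeat kept | 3.4% | 7.9% | 2.3 |
| Filter, one repeat, first value kept | 7.4% | 7.9% | 1.07 |

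With *p* from 2.5% to 10% and correlation 0.5 to 0.9, the ratio is about 2.3 to 2.6 with no repeats, 2.1 to 2.6 with only the repeat kept, and 1.05 to 1.09 with the first value kept. At *p* = 2.5% and correlation 0 to 0.85, the no-repeat ratio is 2.4 to 2.9.

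**Step 3: calcitonin.** With no repeats the pre-dose figure is 0%, and the Day 7 figure is 1.1% to 7.5% over *p* = 2.5% to 10% and correlation 0.5 to 0.9. If a cleared first value is counted, *p* = 2.5% and correlation 0.7 give about 1.7% before and 2.1% after.

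**Step 4: what one arm would show.** At a post-dose rate of 3.4% (*p* = 2.5%, correlation 0.7, no repeats), the chance of any post-dose case of a given analyte is 1 − 0.966¹⁵ = 40% in an arm of 15 and 1 − 0.966¹⁰ = 29% in the placebo arm.

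**Step 5: does the Day 1 draw cure it?** After the filter, Days 1, 3, 5 and 7 have equal expected incidence (1.3% each at *p* = 2.5%, correlation 0.7). Shifts from normal to high and from high to normal between Day 1 and any one later day then balance in expectation. A count of subjects normal on Day 1 and high on any later day does not balance: it starts at 0% by definition and reaches about 2.9% in the same model.

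**The case against.** The strongest reply is that the table already carries its control. Selection comes before randomization (footnote q: "Randomization will occur after all Check-In assessments are performed and results are reviewed at pre-dose on Day 1"), so it is the same in every arm in expectation, and the placebo column sits alongside. SAP 3.6.2 also gives change from baseline at each visit. For chemistry, SAP 3.1.3 makes that baseline the last pre-dose assessment, normally Day 1. All of this stands, and it limits the point to the within-arm comparison.

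The repeat rule also stands as an objection to any large figure. SAP 3.1.2 analyses scheduled visits and generally only lists unscheduled ones. If a repeat is recorded as unscheduled, the first value stays in the table and the liver-test artefact nearly vanishes. The documents do not say how a repeat is classed.

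The scope is narrow. The ULN filter reaches the high side of four chemistry analytes plus calcitonin. For TSH the wording ties the limit to uncontrolled thyroid disease, so the filter is arguable. Triglycerides are cut at a fixed 500 mg/dL. Exclusion 25 removes other values only on the investigator's judgement. In Exclusion 24, the words naming Screening or Check-In follow the renal clause, and it is unclear whether they also govern the liver tests.

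A reader might infer three stronger things, none of which the documents support:
- *Abnormalities will rise in every arm.* The rise is an expectation. By Step 4, an arm of 15 more often shows no post-dose case of a given analyte than any.
- *Calcitonin is zero before dosing by design.* That holds only if a first value cleared on repeat is not counted.
- *Cases on drug with none on placebo would be a product of the filter.* In the Step 4 model, an active arm of 15 shows at least one case while placebo shows none with probability 0.40 × 0.71 = 29% with the filter, and 32% without it. That pattern comes from small, unequal arms.

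**Conclusion.** The point holds in limited form. For high ALT, AST, ALP, total bilirubin and calcitonin, and arguably TSH, the pre-dose count is lowered by eligibility, and the within-arm before/after incidence is biased upward in expectation.

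For the liver tests, the expected rise runs from about 1.05-fold (first values kept after a normal repeat; slightly less if draws are independent) to about 2.9-fold (no repeats). The size rests on assumed rates and correlations and on two matters the documents leave open: which value counts after a repeat, and at which visits the liver limits apply. The active-versus-placebo comparison is unbiased and the primary analysis is unaffected. This is an inexpensive improvement to a descriptive safety table.

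**What to change.** In SAP 3.6.2:
- Replace the pooled before/after incidence with low/normal/high shift tables by arm, placebo alongside, from the SAP baseline to each of Days 3, 5 and 7 separately, showing shifts in both directions. For chemistry, hematology and coagulation the baseline is the Day 1 pre-dose draw. The same applies to urinalysis once its Day 1 sample is confirmed as pre-dose, since its row in Table 2 does not carry footnote o.
- State whether the first or the repeat value enters the table when an eligibility test is repeated.
- If newly abnormal subjects (normal on Day 1) are counted, say that the count is to be read only against placebo.
- For calcitonin and TSH, which have no Day 1 draw, show Day 7 by arm with a footnote that Screening values were restricted by eligibility.

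The protocol team should also confirm which visits the liver-test clause of Exclusion 24 covers, so that the footnotes are accurate.

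The cost is SAP wording, one revised table shell and a few more rows per analyte. No new data are needed.

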### 3.6.3 Vital Signs

Vital signs will be summarized using descriptive statistics at the scheduled visits and/or timepoints that are specified within the Schedule of Events within the Protocol. The vital signs parameters to be summarized are the following:

- Systolic Blood Pressure
- Diastolic Blood Pressure
- Heart Rate
- Respiratory Rate
- Temperature

Observed values and change from baseline will be presented at each scheduled visit and/or timepoint and baseline by vital sign.

All vital sign data will be listed.

#### 3.6.4 *Electrocardiograms*

Electrocardiogram (ECG) data will be summarized using descriptive statistics at the scheduled visits and/or timepoints that are specified within the Schedule of Events within the Protocol. The electrocardiogram parameters to be summarized are the following:

- Heart Rate
- PR Interval
- RR Interval
- QRS Duration
- QT Interval
- QTcF Interval

The average value of the collected triplicates will be calculated for each parameter at each timepoint and will be used for all summary statistics for numeric parameters. The “worst” triplicate value for overall interpretation at each timepoint will be used for all categorical summaries.

Observed values and change from baseline will be presented at each scheduled visit and/or timepoint and baseline by electrocardiogram parameter.

The overall interpretation and clinical significance of the interpretation will be summarized with counts and percentages at each scheduled visit and/or timepoint.

All ECG data will be listed.

#### 3.6.5 *Physical Examinations*

All physical examination data will be listed.

#### 3.6.6 *Injection Site Reactions*

The toxicity of injection site reactions will be summarized with counts and percentages at the scheduled visits and/or timepoints that are specified within the Schedule of Events within the Protocol.

The injection site reaction parameters to be summarized are the following:

- Pain
- Tenderness
- Erythema/Redness
- Induration/Swelling

All injection site reaction data will be listed.

#### 3.6.7 *Columbia-Suicide Severity Rating Scale*

All data from the C-SSRS will be listed.

#### 3.6.8 *Other Safety Assessments*

Observed values and change from baseline values nausea scores on a VAS (0 to 100 mm) will be summarized using descriptive statistics for all measured visits and timepoints.

The area under effect (AUE) will also be calculated from time 0 to 6.5 hours (390 minutes) for the nausea scale on Day 1 and Day 7.  $AUE_{0-6.5}$  will be calculated using the trapezoid method. If any observations are missing for the scheduled timepoints for the AUE calculation, the missing values will be imputed using the LOCF method.

## 4 ANALYSIS TIMING

### 4.1 Interim Analysis

No interim analysis is planned for this study.

### 4.2 Pre-Final Analysis

After the database is locked and exclusions from analysis populations have been finalized, the randomized treatment assignments will be unblinded and the pre-final analysis will be generated. Pre-final Tables, Figures, and Listings (TFLs) will be provided approximately 3 weeks after database lock.

### 4.3 Final Analysis

Final TFLs will be provided approximately 1 week after Sponsor comments are returned on the Pre-Final TFLs. Any comments or edits from pre-final analysis will be implemented for final analysis. If there were no changes to the pre-final analysis or the study database, the pre-final TFLs may be considered final. In addition to TFLs, SDTM data and ADaM data along with associated files will be provided. Associated files may include annotated case report forms (CRFs), SDTM specifications, SDTM programs, ADaM specifications, ADaM programs, TFL programs, and CDISC Define packages for both SDTM and ADaM data.

## 5 CHANGES FROM PROTOCOL-SPECIFIED STATISTICAL ANALYSES

The mixed model of repeated measures within section 9.2.1.1 of the protocol was updated in version 2.0 of the SAP. Change from baseline of food (weight and energy content) consumed during lunch was removed from the planned study analyses. Baseline food consumption was also removed as a covariate. These analyses cannot be completed, as food (weight and energy content) consumed during lunch is not collected prior to first dose of study drug.

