##### **9.2.1.1 Primary efficacy analysis**

For each treatment group, descriptive statistics will be calculated at each visit for amount of food (weight and energy content) consumed during lunch.

Absolute and change from baseline will each be analyzed using a mixed model of repeated measures approach using a significance level of  $\alpha = 0.1$ . Fixed effects for the model will be baseline, treatment, visit, and treatment-by-visit interaction with a random effect for subject. Least squares mean values, differences in least squared means values, standard errors, p-values, and 90% confidence intervals will be presented.

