
- r. Study drug will be administered 30 minutes before lunch as a single SC injection in the abdominal skin; the injection site location in the abdomen will be rotated at each administration.
- s. Injection site reactions will be considered AEs and will be assessed on Day 1 at 0.5, 1, 2, 3, 4, 6, and 8 hours post-dose and once daily on Days 2 through 7 at 1.5 hours ( $\pm 30$  minutes) post-dose.
- t. The start time of the standardized lunch will be 30 minutes post-dose; start time will be recorded. Subjects will consume as much of the standardized lunch as desired, and food will be weighed prior to and after eating to assess food intake.
- u. On Days 1 through 7, the VAS questionnaire to evaluate hunger, satiety, prospective consumption, desire to eat, and nausea will be administered pre-dose; 20 ( $\pm 5$ ) minutes after study drug administration; and 1.5, 2.5, 3.5, 4.5, 5.5, and 6.5 hours ( $\pm 5$  minutes) after study drug administration. On Day -1, the VAS questionnaire to evaluate hunger, satiety, prospective consumption, desire to eat, and nausea will be administered 10 ( $\pm 5$ ) minutes prior to the start of lunch and 1, 2, 3, 4, 5, and 6 hours ( $\pm 5$  minutes) after the start of lunch. On Day -1 and on Days 1 through 7, the VAS questionnaire to evaluate palatability will be administered at the start of lunch.
- v. Finger stick blood glucose monitoring for hypoglycemia (defined as blood glucose value  $< 54$  mg/dL [ $< 3.0$  mmol/L]) will be conducted at 1 and 2 hours after each dose on Days 1 through 7 and as needed for symptoms of hypoglycemia (ie, dizziness or light-headedness, blurred vision, anxiety, irritability or mood changes, fast heartbeat, sweating, slurred speech, hunger, confusion or drowsiness, feeling jittery, shakiness, weakness, headache).
- w. AEs will be monitored and documented from the time of informed consent until study participation is complete. Any medical condition already present at the time of informed consent should be recorded as medical history and not be reported as an AE unless the medical condition or signs or symptoms present at baseline change in severity, frequency, or seriousness at any time during the study. In this case, it should be reported as an AE.

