### 2.2 Study Design

#### 2.2.1 Overview

This is a randomized, placebo-controlled, double-blind, parallel-group Phase 2 study evaluating the efficacy, safety, and PK of daily administrations of the GLP-1 analogue ROSE-010 on appetite and food intake in overweight and obese female subjects. The study is planned to include 3 parallel treatment groups, with 40 subjects randomized in a 3:3:2 ratio to receive ROSE-010 99 mcg, ROSE-010 150 mcg, or placebo, respectively, as follows:

- Treatment Group 1: 99 mcg ROSE-010 (15 subjects) administered SC once daily for 7 consecutive days.
- Treatment Group 2: 150 mcg ROSE-010 (15 subjects) administered SC once daily for 7 consecutive days.
- Treatment Group 3: Placebo (10 subjects) administered SC once daily for 7 consecutive days.

For each subject, the study will consist of the following:

- Screening Period (Day -28 to -2) and Check-In (Day -1), during which subjects will be evaluated for eligibility.
- Treatment Period (Day 1 to Day 7), during which subjects will receive 7 once-daily doses of ROSE-010 or placebo, followed by discharge on Day 8.
- Follow-up phone call, which will be completed 7 ( $\pm$ 2) days after the final dose of study drug.

Consenting subjects will be screened for eligibility according to study-specific inclusion/exclusion criteria within 28 days prior to the first administration of study drug (Day 1). Subjects will be admitted to the CPU on Day -1 and will remain confined to the CPU until discharge on Day 8/Early Termination (ET). On Day 1, subjects will be randomized in a 3:3:2 ratio to receive ROSE-010 99 mcg, ROSE-010 150 mcg, or placebo, respectively. Study drug will be administered SC once daily (30 minutes before lunch) for 7 consecutive days (Days 1 to 7). All meals served at the CPU will be standardized and controlled. Subjects will consume as much of the standardized lunch as desired, and food will be weighed prior to and after eating to assess food intake. Assessments of hunger, satiety, prospective consumption, desire to eat, palatability, and nausea will be performed. Blood samples will be collected to evaluate PK. Safety parameters will be monitored.

Subjects will be discharged on Day 8/ET. The end of study follow-up phone call will be completed 7 ( $\pm$ 2) days after the final dose of study drug.

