##### *3.5.1.1 Primary Efficacy Analysis*

For each treatment group, descriptive statistics will be calculated at each visit for amount of food (weight and energy content) consumed during lunch.

Observed values will be analyzed using a mixed model of repeated measures approach using a significance level of  $\alpha = 0.1$ . Fixed effects for the model will be treatment, visit, and treatment-by-visit interaction with a random effect for subject. Least squares mean values, differences in least squared means values, standard errors, p-values, and 90% confidence intervals will be presented.

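### Lunch intake is not measured on Day -1, so the primary model loses its planned baseline covariate and gets no substitute: a precision loss of uncertain size, not a bias

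*SAP*

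**What the plan says.** Protocol 9.2.1.1 analyses both absolute lunch intake and its change from baseline in a repeated-measures mixed model: "Fixed effects for the model will be baseline, treatment, visit, and treatment-by-visit interaction with a random effect for subject".

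The Schedule of Events (Protocol Appendix A, Table 2) marks food intake on Days 1 to 7; the Check-In (Day -1) cell is empty. Yet a lunch takes place that day. Footnote u times the appetite scales from 10 minutes before it to 6 hours after its start, and adds: "On Day -1 and on Days 1 through 7, the VAS questionnaire to evaluate palatability will be administered at the start of lunch".

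SAP version 2.0 removes the change-from-baseline analysis and the covariate. Its section 5 explains: "These analyses cannot be completed, as food (weight and energy content) consumed during lunch is not collected prior to first dose of study drug". The primary model in SAP 3.5.1.1 now reads: "Fixed effects for the model will be treatment, visit, and treatment-by-visit interaction with a random effect for subject". No other baseline variable takes the vacant place. Significance is at 0.10, and "p-values, and 90% confidence intervals will be presented".

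The design in SAP 2.2.1 is parallel-group, "with 40 subjects randomized in a 3:3:2 ratio to receive ROSE-010 99 mcg, ROSE-010 150 mcg, or placebo, respectively".

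**The concern.** People differ in how much they eat when free to choose, and a parallel-group comparison carries those differences in full. The random subject effect accounts for the correlation among one subject's seven lunches. It does not take between-subject variance out of the treatment contrast, because each subject receives only one treatment. A pre-dose measure of the same behaviour is the usual way to remove part of that variance and to correct a chance difference in habitual intake between arms, which is a real possibility with 10 subjects on placebo.

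The protocol planned for this and the Schedule made it impossible. The appetite and palatability scales have a Day -1 lunch assessment; the primary endpoint has none. At stake is the width of the confidence intervals for the primary comparison.

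**Working it through.** **What can be reproduced.** The plan states no power, SD, effect size or precision target, and no formal sample size calculation was done (SAP 2.2.4), so there is no planning figure to check. The internal figures agree: 40 × 3/8 = 15 per active arm, 40 × 2/8 = 10 on placebo, and a two-sided level of 0.10 matches 90% intervals.

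**Inputs.** From the documents: 15 versus 10 per contrast, three arms, seven daily lunches. Assumed: a common correlation ρ between any two days' lunches for the same subject (the structure that a random subject effect implies), over the range 0.3 to 0.7, and a Day -1 lunch that is the same kind of meal. Results are in units of the single-day between-subject SD.

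**Formulas.**
- Single day, unadjusted: SE = √(1/10 + 1/15) = 0.408.
- 7-day average: its variance is v = (1 + 6ρ)/7, so SE = √[v(1/10 + 1/15)].
- Share of variance explained by one Day -1 measurement: R² = ρ² for a single day, and R² = ρ²/v = 7ρ²/(1 + 6ρ) for the average.
- Estimating the slope with 40 subjects and three arms multiplies the variance by about 1 + 1/35. The net variance ratio is (1 − R²)(1 + 1/35).

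**Example, ρ = 0.5.** Single day: 0.75 × 1.0286 = 0.771, so 23% is removed. Average: v = 4/7 = 0.571 and R² = 0.25/0.571 = 0.4375; then 0.5625 × 1.0286 = 0.579, so 42% is removed.

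| ρ (assumed) | Contrast | SE without covariate | SE with covariate | Variance removed, net | Unadjusted total N giving the same precision |
|---|---|---|---|---|---|
| 0.3 | single day | 0.408 | 0.395 | 6% | 43 |
| 0.5 | single day | 0.408 | 0.359 | 23% | 52 |
| 0.7 | single day | 0.408 | 0.296 | 48% | 76 |
| 0.3 | 7-day average | 0.258 | 0.231 | 20% | 50 |
| 0.5 | 7-day average | 0.309 | 0.235 | 42% | 69 |
| 0.7 | 7-day average | 0.352 | 0.208 | 65% | 114 |

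The last column is 40 divided by the net variance ratio. A simulation of 10,000 trials with arms of 10, 15 and 15 gave 6%, 23% and 46% for a single day and 19%, 42% and 64% for the average. At ρ = 0.2 the single-day gain is only 1%.

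**In terms of power.** For an assumed single-day effect of 0.8 SD at two-sided 0.10 (non-central t, 37 or 36 degrees of freedom), power is 61% unadjusted, and 63%, 71% or 84% adjusted at ρ = 0.3, 0.5 or 0.7.

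**Change from baseline.** A single-day change score without the covariate has variance 2(1 − ρ) times the unadjusted one: 1.4, 1.0 and 0.6 at the three correlations. It loses precision below ρ = 0.5. With baseline also in the model, as the protocol planned, the change and absolute analyses give the same treatment difference, because subtracting baseline only shifts its slope by 1. The covariate is what is worth recovering.

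**The case against.** The SAP does not hide the change: both its version history and section 5 record it, and section 5 gives the reason. A reader might infer that the unadjusted result is biased. It is not biased on this account, since randomization protects the comparison with or without the covariate. The study describes itself as exploratory and sets no precision target. All of this stands, and it limits the matter to efficiency and chance imbalance.

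A reader might also infer that much of the achievable precision has been lost. The documents give no correlation to support that. If Day -1 intake correlated 0.6, 0.7 or 0.8 with the 7-day mean, the difference detectable with 80% power would fall from 1.03 SD of that mean to 0.83, 0.74 or 0.62 (before the small slope cost). But a day-to-day correlation of 0.3 implies only √(0.09/0.4) = 0.47, and a fall to about 0.92. Nor is the 7-day average the stated endpoint: SAP 2.3.1 defines intake on each treatment day, where the gain is smaller.

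Finally, weighing the Day -1 plate might look like the whole remedy. The instructions on eating as desired and weighing in Protocol 7.2.1 and footnote t are attached to the lunch 30 minutes after dosing. The design summary in Protocol 3.1 is more general, but nothing states that the admission-day lunch is the same free-choice meal. If it is not, its correlation with later lunches may be lower.

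What survives is that a planned covariate was lost through a scheduling omission and nothing was put in its place.

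**Conclusion.** The point holds as a loss of precision and of protection against chance imbalance. Over an assumed day-to-day correlation of 0.3 to 0.7, the variance that a Day -1 covariate could have removed is 6% to 48% for the stated single-day contrasts and 20% to 65% for the 7-day average. These figures rest on equal correlation between days and on a comparable Day -1 meal. Calling the loss large is fair from a correlation of about 0.5 upward, but not for single days at 0.3 or below.

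The documents do not support reading this as a biased analysis, an undisclosed change or a flaw that invalidates the primary comparison. It is a precision improvement for an exploratory study and should be ranked as such.

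**What to change.** The documents do not show how far recruitment has gone; SAP version 2.0 is dated 19 February 2025. The remedy depends on that.

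1. **If no subject, or only a few, have passed Day -1:** add a food-intake mark at Check-In in the Schedule. State that this lunch is the same standardized, free-choice meal, weighed before and after. Restore Day -1 intake as a covariate in SAP 3.5.1.1, without reinstating change from baseline. State a rule for subjects who lack the value, because software by default drops records with a missing covariate; one option is to substitute the mean of the observed Day -1 values pooled over arms. The cost is a minor amendment and one more weighed lunch per subject.

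2. **Otherwise:** unweighed lunches cannot be recovered. Add to SAP 3.5.1.1 one fixed, named set of baseline covariates collected for every subject, for example Check-In body weight and the Day 1 pre-dose hunger score, which is the baseline for that scale under SAP 3.1.3. Name the variables outright, with no choice left open, before database lock and the unblinding that follows it (SAP 4.2). The cost is SAP wording and 1 to 2 degrees of freedom. The gain cannot be computed from the documents and may be small.

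In either case, bring Protocol 9.2.1.1 into line with the model that will be run.
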